6.4. Validation Plan

Level 2 validation plan will be implemented for programs creating the STDM and ADaM datasets and at least level 1 for output programs.

7. SUMMARY OF STUDY POPULATION

7.1. Subject Disposition

The disposition summary will include the following:

- All Subjects who provided informed consent.
- All Subjects who failed screening along with the reasons.
- All Subjects in the ITT analysis set
 - Number and percentage of study completion and early discontinuation.
 - Number and percentages of reasons for early discontinuation. Percentages are based on the ITT analysis set.
- All Subjects in the Safety analysis set.
- All Subjects in the mITT analysis set.
- All Subjects in the FAS analysis set.

- All Subjects in the Per-Protocol (PP) analysis set.
- Reasons for Subjects excluded from the mITT, FAS, and Per-Protocol (PP) analysis sets. Percentages are based on the ITT analysis set.

A consort diagram describing Subject enrollment and disposition will be provided. Reasons for Subjects excluded from the mITT analysis set include: not meeting the inclusion/exclusion criteria; area of clean, healthy, and viable wound bed is greater than 2/3 of the wound bed surface area; did not receive any treatment; or did not have the primary endpoint assessment on Day 6-9. Reasons for Subjects excluded from the PP analysis set also include having protocol deviations that impacts the primary analysis.

7.2. Clinical Investigation Plan Deviations

Protocol deviations will be defined as departures from the study protocol that could potentially affect clinical results or safety conclusions. All protocol deviations will be identified, recorded, and presented in Subject data listings.

The clinical study team will review the protocol deviation data and identify and document all disqualifying protocol deviations prior to the final database lock. All disqualifying protocol deviations for the PP analysis set will be presented in listings and will be summarized by coded term/description based on the ITT analysis set.

7.3. Baseline and Demographic Characteristics

Demographics, baseline characteristics and treatment compliance will be presented by treatment arm, and based on the overall mITT, FAS, and PP analysis sets.

Medical history summaries will be presented by treatment arm and overall using the FAS, and mITT populations.

7.3.1. Demographics

Baseline demographics and other characteristics (e.g., age, sex, race, ethnicity, height, weight, body mass index (BMI)). Age and BMI will be compared between the treatment arms using a two-sample t-test (Wilcoxon sum rank test will be used instead if distribution is significantly skewed). Race/ethnicity and sex will be compared between the treatment arms using Fisher's exact test as appropriate.

7.3.2. Baseline Characteristics

Baseline wound assessment by the investigator, which includes the need for bedside eschar debridement along with the debridement type, wound length, width, and estimated percentage of clean, healthy and viable wound bed surface, wound odor, presence of undermining, depth of undermining at maximum undermined area (cm), percentage of wound margin with undermining present.

7.3.3. Medical History

Baseline comorbidities will be summarized and compared between the two treatment arms using Fisher's exact test as appropriate.

All captured medical history, which will be coded using a MedDRA coding dictionary version 23.0 or higher, will be summarized by System Organ Class and Preferred Term based on the FAS and mITT analysis set. Incidence of medical history that can impact wound healing will also be provided, which includes diabetes, peripheral vascular disease, COPD, anemia, local/systemic infection, cancer, poor nutrition, and aging, etc.

7.4. Treatment/Device Use Duration and Compliance

Treatment duration will be computed as the number of days from randomization to the last treatment day: (Last Treatment Date-Randomization Date +1). If the last treatment date is missing, the day of last study visit will be used. Testing for differences between the two treatment arms will be carried out using a two-sample t-test (Wilcoxon sum rank test will be used instead if distribution is significantly skewed).

Treatment duration, number of treatment applications and/or dressing changes per Subject will be summarized by treatment group (collagenase ointment and VFCC) and overall.

Treatment duration will be computed as the number of days from randomization to the last treatment day: (Last Treatment Date-Randomization Date +1).

8. EFFICACY ANALYSIS

8.1. Primary Efficacy Analysis

The primary endpoint is the change in the percent of wound bed surface area (cm^2) considered to be clean, healthy, and viable from baseline to Day 6-9 upon the final dressing removal. The percentage of clean, healthy, and viable tissue (pctCHV) is defined as the sum of percentages of viable Bone/Cartilage/Ligament/Tissue (B/C/L/T), viable fat, viable muscle/fascia, and granulation tissue. The change in percent (ΔpctCHV) of clean, healthy, and viable tissue from baseline to Day 6-9 upon the final dressing removal is defined as:

$$\Delta\text{pctCHV} = \text{pctCHV}_4 - \text{pctCHV}_0$$

where,

pctCHV₀ = percent of clean, healthy, and viable tissue at baseline

pctCHV₄ = percent of clean, healthy, and viable tissue at Day 6-9 upon final dressing removal.

The following hypothesis will be tested:

Null: $\Delta\text{pctCHV}_{\text{VFCC}} - \Delta\text{pctCHV}_{\text{Control}} = 0$
 $\neq 0$

Alternative: $\Delta\text{pctCHV}_{\text{VFCC}} - \Delta\text{pctCHV}_{\text{Control}}$

where $\Delta pctCHV_{VFCC} - \Delta pctCHV_{Control}$ is the difference of the change in percent of wound bed surface area (cm^2) considered to be clean, healthy, and viable between the VFCC with NPWTi-d group and the Control group.

Generalized linear modeling will be used to analyze the primary endpoint with the following fixed effects: clinical site; baseline percent of wound bed surface considered clean, healthy and viable [pctCHV0]; body mass index [BMI]; treatment arm and indicator of baseline wound undermining.

If any of the covariates (except treatment arm and site ID) is not statistically significant at the 0.1 level, then the non-significant term(s) will be removed from the model and the updated model will be re-run. The analysis will be conducted at the α -level determined by the O'Brien-Fleming α -spending function² and observed fraction time.

```
proc mixed data=adeff;
  class trtp siteid undermin;
  model chg=bmi base trtp siteid undermin / ddfm=kr cl;
  lsmeans trtp/ diff cl;
run;
```

The analysis will be conducted at a final alpha level as determined by the O'Brien-Fleming α -spending function². The primary analysis will be based on the mITT analysis set, and the test of the difference of the least square means estimates.

Additionally, a line plot and/or scatterplot and/or boxplots showing the mean or observed percentage in the wound bed surface area considered to be clean, healthy, and viable by treatment arm over time will be generated to display the results from the analyses of the primary endpoint in the FAS, mITT and PP analysis sets.

The following supportive analyses will be conducted in the primary endpoint:

- Repeat the primary analysis on the FAS analysis set using Next Observation Carried Back (NOCB) and Last Observation Carried Forward (LOCF) method, that is, FAS (with NOCB/LOCF imputation).
- Repeat the primary analysis on the Per-Protocol analysis set

If appropriate, supportive/exploratory analyses of the primary endpoint will include:

- A proportional odds logistic regression model (ordered logit link function) with quartile or quintile groupings of the data
- Wilcoxon Rank-Sum test without adjusting for covariates like wound undermining
- Analyses comparing the treatment groups considering covariates (e.g., age, race/ethnicity, sex, and comorbidities)
- Other analyses deemed appropriate to examine unexpected interaction terms including, but not limited to, impact of the Covid pandemic.

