### **8.6. Interim Analysis**

A nonbinding, unblinded interim analysis will be performed when approximately 30 evaluable subjects have had their assessments for the primary endpoint (percent change on wound bed surface area considered to be clean, healthy and viable from baseline to

Day 6-9). The purpose of the interim analysis is to evaluate the need for early stopping due to futility, efficacy, and/or sample size re-calculation.

The primary endpoint will be analyzed as outlined in Section 8.3.4. If the resulting p-value for the primary analysis is less than  $\alpha=0.006$  as determined utilizing the O'Brien-Fleming  $\alpha$ -spending function (O'Brien 1979), the null hypothesis will be rejected, and the study may be stopped for efficacy.

If the null hypothesis could not be rejected, conditional power will be calculated to assess for futility and/or sample size adjustment. If the conditional power is lower than the pre-specified boundary in the interim SAP, the trial may be stopped for futility. If the conditional power is above the futility boundary, the conditional power will be evaluated utilizing methods described in Chen et al (Chen 2004) to determine if a sample size increase is required.

The final analysis will be conducted at  $\alpha=0.048$  to maintain the overall type I error rate at  $\alpha=0.05$  as determined by the O'Brien-Fleming spending function. Details of the interim analysis will be described in the interim SAP before the interim analysis is conducted.

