8.2. Secondary Efficacy Analysis

The secondary efficacy analyses will be conducted to ensure that the family-wise error rate is controlled using the Holm method for multiplicity adjustment. The following are the relevant secondary analyses of interest:

(Between-Treatment Testing)

1. The change in percent of wound surface area with clean, healthy, viable tissue (%) at the Day 4-6 interim visit relative to baseline between the treatment arms.
2. The change in percent of wound surface area with clean, healthy, viable tissue (%) at the Day 2-3 interim visit relative to baseline between the treatment arms.
3. Percent change in total wound area (%) from baseline to Day 6-9 upon the final dressing removal between the treatment arms
4. Percent change in total wound area (%) from baseline to Day 4-6 between the treatment arms
5. Percent change in total wound area (%) from baseline to Day 2-3 between the treatment arms
6. Percent change in total wound volume (%) from baseline to Day 6-9 upon the final dressing removal between the treatment arms
7. Percent change in total wound volume (%) from baseline to Day 4-6 between the treatment arms
8. Percent change in total wound volume (%) from baseline to Day 2-3 between the treatment arms
9. Physician assessment of the need for surgical debridement upon completion of study treatment up to Day 6-9

(Within-Treatment Testing)

10. Within-treatment-arm changes in percent of wound surface area assessed as clean, healthy, viable tissue (%) at the Day 6-9 visit to baseline for VFCC arm.
11. Within-treatment-arm changes in percent of total wound area (%) at the Day 6-9 visit to baseline for VFCC arm.
12. Within-treatment-arm changes in percent of total wound volume (%) at the Day 6-9 visit to baseline for VFCC arm.

8.2.1. Change in percent of wound surface area with healthy/viable/clean tissue relative to baseline

The analysis conducted as primary analysis will be repeated for Day 4-6 and Day 2-3 results. These analyses will be carried out for the mITT and FAS (with NOCB/LOCF imputation).

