8.2.2. Percent change in total wound area (cm^2) relative to baseline

The percent change in total wound area ($\Delta\text{pctArea}$) from baseline to Day X upon the final dressing removal is defined as the difference in total wound area between the Day X assessment and baseline assessment, divided by the baseline value and multiplied by 100.

$$\Delta pctArea = \left(\frac{AreaX - Area0}{Area0} \right) \times 100$$

where,

Area0 = the total wound area at baseline

AreaX = the total wound area at Day X (e.g. Day 6-9) upon final dressing removal.

The following hypothesis will be tested:

Null: $\Delta pctArea_{VFCC} - \Delta pctArea_{Control} = 0$
 $\neq 0$

Alternative: $\Delta pctArea_{VFCC} - \Delta pctArea_{Control}$

where $\Delta pctArea_{VFCC} - \Delta pctArea_{Control}$ is the difference of percent change in total wound area (cm^2) between the VFCC with NPWTi-d group and Control group.

The appropriate generalized linear modeling will be used to analyze the endpoint with potential fixed effects: clinical site; baseline total wound area; body mass index [BMI]; treatment arm and indicator of baseline wound undermining. These analyses will be carried out for the mITT and FAS (with NOCB/LOCF imputation).

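### SAP 8.1 drops covariates at p ≥ 0.1 on the same data it then tests, so the primary test modestly exceeds its level (simulated 4.9–6.4% at 0.048, against 4.6–5.0% with all covariates kept)

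*SAP*

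**What the plan says.** SAP 8.1 lists five fixed effects for the primary analysis: clinical site, pctCHV0, BMI, treatment arm and an indicator of baseline undermining. It sets a condition for dropping terms: "If any of the covariates (except treatment arm and site ID) is not statistically significant at the 0.1 level". What follows when a covariate meets that condition is also stated: "then the non-significant term(s) will be removed from the model and the updated model will be re-run". The primary test is the difference in least-squares means from the resulting model, on the mITT set.

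On the level, the SAP relies on O'Brien-Fleming spending at the observed information fraction ("The analysis will be conducted at a final alpha level as determined by the" that function), and gives no number. Protocol 8.6 gives 0.006 at the interim look and 0.048 at the end, the latter chosen "to maintain the overall type I error rate at" 0.05. Neither document makes any allowance for choosing covariates.

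The supportive analyses in SAP 8.1 repeat the primary analysis on the FAS and on the Per-Protocol set ("Repeat the primary analysis on the Per-Protocol analysis set"). SAP 8.2.1 carries it to the earlier visits: "The analysis conducted as primary analysis will be repeated for Day 4-6 and Day 2-3 results". All of these inherit the rule. No listed analysis is stated to keep all three covariates. A "Wilcoxon Rank-Sum test without adjusting for covariates like wound undermining" is free of the selection, but it is listed only if appropriate and is not the primary test.

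**The concern.** The p-value and interval from the refitted model are calculated as if that model had been fixed in advance, but its covariates were chosen by looking at the outcome. A covariate that stays in has, in part, happened to explain the outcome in this sample, so the residual variance looks too small. When a covariate drops out, the standard error ignores any chance imbalance between arms on it. Both effects push the reported standard error down.

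The setting is small. With 46 evaluable subjects and 15 sites, the full model leaves 46 − 15 − 1 − 3 = 27 residual degrees of freedom. At stake is whether a primary result close to the boundary can be read at its stated level.

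**Working it through.** **The plan's own figures, reproduced.**
- Sample size (SAP 6.2: difference 20, SD 22): P(X>Y) = Φ(20 / (22√2)) = 0.740. Noether's formula, (1.960 + 0.842)² / (3 × 0.240²), gives 45.5 with unrounded inputs, so 23 per group. Allowing for 23% loss, 46 / 0.77 = 59.7, so 60.
- Alpha (Protocol 8.6): at fraction 30/60, 2 − 2Φ(1.96/√0.5) = 0.0056, and the matching final level is 0.0478. These round to the stated 0.006 and 0.048.
- Alpha by the SAP's route: if the final set is 46 evaluable, the fraction is 30/46 = 0.652. The same function then gives 0.015 at the interim and 0.044 at the end.

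**Type I error by simulation.** The documents supply 60 randomised, 46 evaluable, about 15 sites, 1:1 permuted blocks within site, the baseline cap of 2/3 (SAP 5.4), the 0.1 threshold and a two-sided test. Covariate strength, site sizes, block size and the prevalence of undermining are not given, so they were varied. Each null trial was randomised within site and subjects were lost at random. Least squares was fitted with site fixed effects, covariates with p ≥ 0.1 were removed in one step, and treatment was retested.

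| Final test at 0.048 | Rule | All kept |
|---|---|---|
| Linear model, 192 scenarios, 100,000 trials each | 4.9–6.4% | 4.6–4.9% |
| Percentages bounded at 0–100 with capped baseline, 256 scenarios, 60,000 trials each | 5.1–6.3% | 4.6–5.0% |

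Monte Carlo standard errors are 0.07 and 0.09 points. The rule's error exceeded the full model's in all 448 scenarios, by 0.2 to 1.6 points.

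A separately coded simulation (46 evaluable, 15 sites; 20,000 to 60,000 trials) shows how the excess depends on covariate strength. The slope is per standardised covariate, in residual SDs, and is equal for all three.

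| Slope | Rule | All kept |
|---|---|---|
| 0 | 5.6% | 4.9% |
| 0.2 | 6.0% | 4.7% |
| 0.35 | 6.3% | 4.9% |
| 0.5 | 5.8% | 4.7% |
| 1.0 | 5.0% | 4.9% |

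The excess is largest for moderately prognostic covariates and nearly vanishes when all are strong. Over all its scenarios this simulation gave 5.0–6.5% against 4.6–5.2%. A smaller run with 12,000 trials per scenario gave 5.2–6.9% against 4.7–5.3%. Reading the rule as stepwise backward elimination gives 5.7–6.3% against 4.6–5.0%.

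**At the SAP's level.** At 0.0443, two separate runs give 5.8% against 4.6% and 5.5% against 4.2%. The absolute rates fall, but the gap stays.

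**Coverage.** At 0.048 the matching interval is nominally 95.2%. In the linear scenarios its coverage with the rule is 100 − 6.4 = 93.6% to 100 − 4.9 = 95.1%.

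**The case against.** The rule is fixed in advance, with a stated threshold, and it never removes site or treatment. It is not discretionary searching. That is true, but pre-specification does not restore the level, because the final test still takes no account of the selection step.

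Baseline may well be strongly related to change, since change is final minus baseline on a bounded scale, and it would then almost always be kept. With a baseline correlation of −0.6 it is dropped in at most 2.6% of trials, yet the rule still gives 4.9–6.0%, because BMI and undermining are still being selected. If those two are unrelated to outcome, the excess is small: 5.3% against 4.7% (46 evaluable, 15 sites), 5.5% against 5.2% (60, 15 sites) and 5.0% against 4.7% (60, 6 sites).

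The figure 0.048 belongs to the protocol, and the SAP's level depends on the observed fraction. This stands, which is why results at 0.044 are shown.

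Over two looks (0.006, then 0.048) the overall error was 5.4–6.9% with the rule and 5.0–5.3% with all covariates kept, so not all of the distance from 5% is due to the rule. That run assumes the same model at both looks and no change in sample size. The interim SAP is a separate document and was not available.

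Three stronger readings are tempting, and the documents do not support them.
- *The treatment estimate is biased.* Arms are randomised, and treatment and site are always kept. Dropping a baseline covariate does not bias the comparison.
- *Every modelling section has the same inflation.* SAP 8.2.2 and 8.2.3 name candidate terms ("The appropriate generalized linear modeling will be used to analyze the endpoint with potential fixed effects: clinical site; baseline total wound area") but contain no removal rule. SAP 8.2.4 and 8.3.3 take their least-squares means from the between-arm final model. SAP 8.3.4 to 8.3.8 carry the rule, but those analyses are exploratory. Error rates in these sections were not simulated.
- *Every listed term should therefore be made compulsory.* The volume model in SAP 8.2.3 lists baseline wound area as its baseline term. That needs checking separately before anything there is fixed.

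**Conclusion.** The concern holds for the primary test in SAP 8.1. With the removal rule its type I error is about 4.9–6.4% at 0.048, against about 4.6–5.0% with all covariates kept. At about 0.044 it is roughly 5.5–5.8% against 4.2–4.6%. The direction does not depend on the scenario. The size does: it rests on assumed covariate strengths, site sizes, block size and undermining prevalence, and it is close to nil if all three covariates are strongly prognostic. The excess is modest and matters mainly for a result near the boundary. The FAS, Per-Protocol, Day 4–6 and Day 2–3 analyses inherit the rule, but their error rates were not simulated. This should be corrected; it does not undermine the design.

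**What to change.** In SAP 8.1, replace the removal sentence with: *Site, pctCHV0, BMI, baseline undermining and treatment arm are retained whatever their p-values.* The change carries by reference to the FAS and Per-Protocol repeats and to the Day 4–6 and Day 2–3 tests in 8.2.1. If the database is already locked, report the full model beside the selected one. The rule fits the full model first, so this needs no new data.

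The cost is one sentence and up to 3 residual degrees of freedom. Simulated power at 0.048 (difference 20, SD 22, 46 evaluable, 15 sites):

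| Covariates related to change | Full model | Rule | Rule with its size held at 4.8% |
|---|---|---|---|
| None | 72–76% | 77–81% | 75–78% |
| Baseline only (−0.6) | 89–91% | not quoted | 90–92% |
| All three (−0.4, 0.25, 0.25) | 85–88% | 85–88% | 83–86% |

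If no covariate is prognostic, the full model falls below the planned figure of about 80%. Part of the rule's apparent advantage there is its excess type I error; at equal size the loss is about 2.5 points. It is about 1 point if only baseline matters, and there is none if all three do.

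### The primary-analysis code requests confidence limits without an alpha setting, so by software default it gives a 95% interval beside a test made at the smaller O'Brien-Fleming final alpha

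*SAP*

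**What the plan says.** SAP 8.1 ties the primary analysis to the O'Brien-Fleming spending function twice. The first statement refers to the observed information fraction. The second reads "The analysis will be conducted at a final alpha level as determined by the" O'Brien-Fleming function. The SAP prints no number for this level.

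Protocol 8.6 does give one: "The final analysis will be conducted at" alpha 0.048, after an interim efficacy level of 0.006, to hold the overall error at 0.05.

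The decision statistic is explicit in SAP 8.1: "The primary analysis will be based on the mITT analysis set, and the test of the difference of the least square means estimates".

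The code printed for that analysis opens with "proc mixed data=adeff". It requests limits on the MODEL statement and again with "lsmeans trtp/ diff cl". None of the PROC, MODEL or LSMEANS statements carries an ALPHA= option.

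The supplied text gives no confidence level for the primary interval. SAP 6 fixes only the number of decimal places for the limits.

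**The concern.** The estimate and interval for the VFCC minus collagenase difference will be read together with the primary p-value. A two-sided test at level alpha agrees with an interval only when the interval has level 100(1 - alpha)%. Here the test is at 0.048 or another value below 0.05, and the interval as coded is at 95%. It is therefore slightly too narrow for the test beside it.

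In a narrow band of p-values the trial would report a non-significant primary result with an interval that excludes zero, and a reader could draw the opposite conclusion from the interval. What is at stake is the consistency of the primary report when the result is borderline.

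**Working it through.** **Inputs**
- Overall two-sided alpha 0.05, interim 0.006, final 0.048 (Protocol 8.6).
- Interim at about 30 evaluable subjects (Protocol 8.6, SAP 6.1). The information fraction t is 30/60 = 0.50 if the denominator is the randomized total, or 30/46 = 0.652 if it is the evaluable total of 2 × 23. The documents do not say which, so the second value is an assumption.
- Difference 40 - 20 = 20 points, SD 22, 23 evaluable per arm (Protocol 8.4.1, SAP 6.2).
- PROC MIXED uses alpha 0.05 for confidence limits when ALPHA= is absent (software default, not in the documents).

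**Step 1. Reproduce the plan's levels.** With the spending form 2 - 2Φ(1.960/√t) at t = 0.50, the interim level is 2 - 2Φ(2.772) = 0.0056. The final level that brings the two-look error to 0.05 (bivariate normal, correlation √t) is 0.0478. These round to the protocol's 0.006 and 0.048.

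**Step 2. Final alpha at the observed fraction.** SAP 8.1 allows the level to move with the fraction. The second usual form is 4 - 4Φ(2.241/√t).

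| t | First form | Second form |
|---|---|---|
| 0.50 | 0.0478 | 0.0490 |
| 30/46 | 0.0443 | 0.0466 |

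Every value is below 0.05, so the mismatch is present whichever applies. The matching interval runs from 95.1% (alpha 0.0490) to 95.6% (alpha 0.0443).

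**Step 3. Width.** For an unadjusted comparison, SE = 22 × √(2/23) = 6.49 with 44 df.

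| Alpha | Critical t | Half-width (points) | Ratio to 95% |
|---|---|---|---|
| 0.05 | 2.015 | 13.07 | 1.000 |
| 0.048 | 2.034 | 13.20 | 1.009 |
| 0.0466 | 2.048 | 13.28 | 1.016 |
| 0.0443 | 2.071 | 13.43 | 1.027 |

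**Step 4. A contradictory result.** A difference of 13.13 points has p = 0.049, which is not significant at 0.048.
- 95% interval: 13.13 ± 13.07, or 0.06 to 26.21. It excludes zero.
- 95.2% interval: 13.13 ± 13.20, or -0.06 to 26.33. It includes zero.

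**Step 5. How often.** The chance is the power at 0.05 minus the power at the final alpha, from the noncentral t with 44 df and noncentrality 20/6.49 = 3.08.
- Final alpha 0.048: 0.8543 - 0.8500 = 0.0043, about 0.4%.
- Final alpha 0.0443: 0.8543 - 0.8414 = 0.0129, about 1.3%.
- At a smaller standardized effect of 0.6 (assumed), the corresponding chances are 0.7% and 2.1%.
- Under the null with alpha 0.048: 0.05 - 0.048 = 0.2%.

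These are fixed-sample figures. Requiring that the trial did not stop for efficacy at the interim lowers them slightly.

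**The case against.** The strongest reply is that nothing is decided by the interval. SAP 8.1 names the test and its alpha, so type I error, power and the primary conclusion do not change. That stands in full.

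A reader might infer from the 95% interval that the trial's overall error exceeds 5%. The documents do not support this. Protocol 8.6 promises 0.05 for the testing procedure, not for interval coverage, and neither document uses exclusion of zero by the interval as a decision rule.

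The code is also a skeleton. It shows no mITT filter, no visit selection and no re-run after covariate removal, all of which the text supplies. The final alpha depends on the observed fraction, so it could not be hard-coded when the SAP was written. This is fair, but the text that fills those other gaps gives no interval level, and a placeholder would have been enough.

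The level could be given in documents not supplied. SAP 12 says the planned tables were moved to a separate file, and SAP 6.1 sends the interim details to an interim SAP. That cannot be excluded. The claim is limited to the supplied protocol and SAP.

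It may also be tempting to count the full analysis set and per-protocol repeats as the same fault. SAP 8.1 calls them supportive. No confirmatory decision rests on them, so a conventional interval there contradicts no rule.

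Finally, a 95% interval beside a group-sequential test is acceptable if it is labelled descriptive. The SAP gives no such label.

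**Conclusion.** The point holds as a minor matter of reporting consistency. As coded, the primary interval is a 95% interval, about 0.9% too narrow for a test at 0.048 and 2.7% too narrow for a test at 0.0443. The chance of a visible contradiction at the design effect is about 0.4% on the protocol's printed level, and up to 1.3% if the information fraction is 30/46.

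The conclusion rests on the PROC MIXED default and on the code being run as printed. The sizes rest on an unadjusted t-test with SD 22 and 23 per arm, and the upper size also on the assumed fraction. A sample-size increase, which Protocol 8.6 permits, would lower the fraction, move the final alpha back towards 0.05 and shrink the gap.

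**What to change.** In SAP 8.1, add alpha=<final alpha> to the LSMEANS statement of the primary mITT analysis, with the value filled in from the same calculation that sets the test level. Do the same on the MODEL statement if those limits are reported. Add one sentence saying that the primary interval is the 100(1 - final alpha)% interval. If a 95% interval is also wanted, show it and label it descriptive. Matching the full analysis set and per-protocol intervals is optional, for consistency only.

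The cost is one code option and one sentence, with an interval about 1% to 3% wider. No data, sample size or procedure changes.
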